3.8.2 Discontinuation of the trial by the sponsor

Boehringer Ingelheim reserves the right to discontinue the trial overall or at a particular trial site at any time for the following reasons:

- 1. Failure to meet expected enrolment goals overall or at a particular trial site.
- 2. Emergence of any efficacy/safety information invalidating the earlier positive benefit-riskassessment that could significantly affect the continuation of the trial.
- 3. Violation of GCP, the CTP, or the contract disturbing the appropriate conduct of the trial.

The Investigator / the trial site will be reimbursed for reasonable expenses incurred in case of trial termination (except in case of the third reason).

Page 32 of 118

Proprietary confidential information © 2016 Boehringer Ingelheim International GmbH or one or more of its affiliated companies

4. **TREATMENTS**

4.1 TREATMENTS TO BE ADMINISTERED

4.1.1 Identity of BI investigational product(s) and comparator product(s)

Table 4.1.1: 1 Nintedanib (investigational drug)

Substance:	Nintedanib
Pharmaceutical formulation:	Soft gelatine capsule
Source:	BI Pharma GmBH & Co. KG
Unit Strength:	150 mg
Posology:	Group 1: Day 1 and Day 23: one 150 mg capsule in the morning
	Group 2: Days 9-15: one 150 mg capsule in the morning and one in the evening
	Day 16: one 150 mg capsule in the morning
Route of administration:	Oral (swallowed) administration with food

Table 4.1.1: 2 Pirfenidone (investigational drug)

Substance:	Pirfenidone
Pharmaceutical formulation:	Capsule
Source:	Roche Registration Limited (previously InterMune
	UK Ltd)
Unit Strength:	267 mg
Posology:	Group 1 Days 2-8: one capsule three times a day Days 9-15: two capsules three times a day Days 16-23: three capsules three times a day
	Group 2 Days 1-15: three capsules three times a day Day 16: three capsules in the morning only
Route of administration:	Oral (swallowed) administration with food

sion 4.0 Page 33 of 118

Proprietary confidential information © 2016 Boehringer Ingelheim International GmbH or one or more of its affiliated companies

4.1.2 Method of assigning patients to treatment groups

Patients are allocated to either Group 1 or Group 2 based on their current treatment at screening. There will be no randomisation required in this trial. Patients who are not being treated for IPF and fulfil all eligibility criteria will enter Group 1. Patients who are chronic users of pirfenidone and fulfil all eligibility criteria will enter Group 2.

4.1.3 Selection of doses in the trial

Nintedanib: A dose of 150 mg bid (total daily dose of 300 mg) was selected for this trial, as this is the recommended dose based on prescribing information in the participating country. Dose adjustments are permitted as described in section 4.2.

Pirfenidone: A dose titrated up to 801 mg tid (total daily dose of 2403 mg) was selected for this trial as this is the recommended dose based on prescribing information in the participating country. Dose adjustments permitted as per section 4.2.

4.1.4 Drug assignment and administration of doses for each patient

Drug is dispensed by the investigator, study coordinator or pharmacist, depending on the site structure. If the patient is currently not being treated for IPF at screening and they fulfil the inclusion/exclusion criteria, they will be assigned manually by the study site personnel to Group 1 and if they are a chronic pirfenidone user at screening and they fulfil the inclusion/exclusion criteria they will be assigned manually by the site to Group 2. There will be no IRT used in this trial. Sites will be required to inform the Sponsor of each screening and each start of treatment using the form provided in the ISF. The Sponsor will monitor recruitment to each group and inform sites when recruitment is close to complete.

Group 1

Visit 2 will be over two days. The patient is not required to stay in the clinic overnight between Day 1 and Day 2. At Visit 2, Day 1, eligible patients will receive one 150 mg nintedanib capsule in the clinic in the morning (Table 4.1.4:2 see Flowchart for Group 1 patients and Section 10.2 for timings of dosing and PK samples). This will be given to the patient by the site staff from a nintedanib bottle (this bottle should be kept at clinic and be used for patients who are in Group 1 for the first and second PK day). Gloves should be worn by the person giving the capsule to the patient and the capsule should be tipped out into a pot where the patient can then pick it up and take it. The patient should swallow nintedanib, unchewed, with food and a glass of water at the clinic.

At Visit 2, Day 2, the patient will return to clinic for their 24 hour PK sample (see Section 10.2) and they will be dispensed three wallets of pirfenidone. The patient will take the first dose at the clinic in the morning with food and a glass of water, under supervision and then go home and continue dosing at home. A dosing card will be provided to the patient, which will explain how they should uptitrate during the trial.

The patient will use the first wallet for 14 days titrating according to Table 4.1.4:1. Once the patient has completed the uptitration then they would use the second wallet and take 3 capsules 3

Boehringer Ingelheim 29 July 2016 BI Trial No.: 1199.229 c03463451-08 **Trial Protocol Version 4.0** Page 34 of 118

Proprietary confidential information © 2016 Boehringer Ingelheim International GmbH or one or more of its affiliated companies

times a day for the next 7 days. Once the patient has had 7 consecutive, stable days on 801 mg tid they would then come to the clinic for the next PK day (Visit 3, Day 23; there is a 6 day window during the uptitration phase and Visit 3. This allows for extending the uptitration if required and ensuring that there are 7 consecutive, stable days at 801 mg tid before the patient returns to clinic for the second PK day Visit 3. The third wallet of pirfenidone can be used if required during this period).

The patient will return to the clinic for Visit 3. They should not take their medication at home, but should bring it to the clinic with them. At the clinic, they will be given their morning dose of 801mg pirfenidone and they will also receive one 150 mg capsule of nintedanib at the clinic with food and a glass of water. They will also be given their second dose of pirfenidone at the clinic at 14:00. They will take their final dose of pirfenidone at 20:00 in the evening at home once they have left the clinic. They should be advised to take this with food and a glass of water. The following day (Visit 3, Day 24), the patient will return to the clinic for their 24 hour PK sample (see Section 10.2). The patient will then have a washout of 28 days where no study medication is taken and then they will return to clinic for the PK Follow-Up visit (see Flowchart).

If the patient does not achieve 7 consecutive, stable days prior to Visit 3 plus the 6 day window then the patient would stop medication and attend the clinic for Visit 3, but would not have the PK samples taken (See Figure 4.1.4:1).

Table 4.1.4:1	Schedule for the titration	phase of pirfenidone	(Group 1)
---------------	----------------------------	----------------------	-----------

Titration Period	Administration	Dose	Total daily Dose
Day 2 to Day 8 of titration	1 capsule tid	267 mg tid	801 mg
Day 9 to Day 15 of titration	2 capsules tid	534 mg tid	1602 mg

Table 4.1.4:2 Quantity of medication kits dispensed to the patient

Group 1

Visit	Nintedanib bottle	Pirfenidone wallet
2	0 (1 capsule given in clinic)	3
3	0 (1 capsule given in clinic)	

Boehringer IngelheimBI Trial No.: 1199.229c03463451-08Trial Protocol Version 4.0

Page 35 of 118

Proprietary confidential information © 2016 Boehringer Ingelheim International GmbH or one or more of its affiliated companies

Table 4.1.4:2Quantity of medication kits dispensed to patient continued

Group 2

Visit	Nintedanib bottle	Pirfenidone wallet
2	0	2
3a	1	1
3b	0	

Group 2

The patient will come to the clinic for Visit 2 (this is not a PK day). They should take their full dose of commercial supply of pirfenidone the previous day and then stop taking their commercial supply. At the clinic, eligible patients will receive two wallets of pirfenidone. The patient will take the first dose at the clinic in the morning with food and a glass of water, under supervision and then go home and continue dosing at home. A dosing card will be provided to the patient which will explain how they should take their study medication during the trial.

Once the patient has had 7 consecutive, stable days on 801 mg tid (3 capsules 3 times a day; this can be reduced to 534 mg tid) they would then come to the clinic for the next PK visit (Visit 3a, Day 8; see flowchart and section 10.2; there is a 3 day window to ensure that the patient has 7 consecutive days at full dose).

The patient will return to the clinic for Visit 3a. They should not take their medication at home, but should bring it to the clinic with them. At the clinic, they will be given their morning dose of 801mg pirfenidone (or 534mg if they have dose reduced) at the clinic with food and a glass of water. They will also be given their second dose of pirfenidone at the clinic at 14:00. They will take their final dose of pirfenidone at 20:00 in the evening at home once they have left the clinic. They should be advised to take this with food and a glass of water. Before they leave the clinic they will be given another wallet of pirfenidone and a bottle of nintedanib to take home (they should also be given the remaining pirfenidone wallet from the previous visit once compliance has been assessed). They will be advised to start the nintedanib with the morning and evening doses of pirfenidone.

For the next 7 days the patient will continue on pirfenidone 801 mg tid (3 capsules 3 times a day; or 534 mg tid) and take nintedanib 150 mg twice a day. Once the patient has had 7 consecutive stable days on 801 mg (or 534 mg) pirfenidone tid and nintedanib 150 mg twice a day then they would come to the clinic for the next PK day (Visit 3b, Day 16; there is a three day window for this visit to allow for 7 consecutive days if required; see Figure 3.1:1).

The patient will return to the clinic for Visit 3b. They should not take their medication at home, but should bring it to the clinic with them. At the clinic, they will be given their morning dose of 801mg pirfenidone and they will also receive one 150 mg capsule of nintedanib at the clinic with

food and a glass of water. The patient will then have a washout of 28 days where no study medication is taken and then they will return to clinic for the PK Follow-Up visit (see Flowchart).

If the patient does not achieve 7 consecutive, stable days prior to visit 3b plus the 3 day window then the patient would stop medication and attend the clinic for Visit 3b, but would not have the PK samples taken (See Figure 4.1.4:1).

Group 1 patients

Figure 4.1.4: 1 Guidance for patients who withdraw or do not tolerate uptitration during the PK evaluation period
Page 37 of 118

Proprietary confidential information © 2016 Boehringer Ingelheim International GmbH or one or more of its affiliated companies

Group 2 patients Day 1-7

Patient can start at either point

Figure 4.1.4:1 Guidance for patients who withdraw or do not tolerate uptitration during the PK evaluation period continued

Page 38 of 118

Proprietary confidential information © 2016 Boehringer Ingelheim International GmbH or one or more of its affiliated companies

Group 2 patients Day 9-15

Patient can start at either point

Figure 4.1.4:1 Guidance for patients who withdraw or do not tolerate uptitration during the PK evaluation period continued

4.1.4.1 Nintedanib and pirfenidone

The Investigator should emphasise to the patient the importance of taking all doses of trial medication in order to avoid missed doses throughout the PK period.

Group 1

- If a dose of pirfenidone is missed, administration should resume at the next scheduled time at the recommended dose. Double doses should not be taken to make up for the forgotten capsules.
- It is recommended that pirfenidone is administered at the same time in the morning and evening with food and a glass of water, with the third pirfenidone dose administered at the midpoint with food and a glass of water.

• If a patient withdraws from the PK period or is unable to tolerate uptitration please refer to Figure 4.1.4:1.

Group 2

- The patient should swallow nintedanib unchewed with food and a glass of water twice daily and should observe a dosing interval of approximately 12 hours.
- If a dose of pirfenidone or nintedanib is missed, administration should resume at the next scheduled time at the recommended dose. Double doses should not be taken to make up for forgotten capsules.
- It is recommended that nintedanib and pirfenidone are administered together at the same time in the morning and evening with food and a glass of water, with the third pirfenidone dose administered at the midpoint with food and a glass of water.
- If a patient withdraws from the PK period or is unable to tolerate uptitration please refer to Figure 4.1.4:1.

Patients experiencing adverse events may require drug interruption or reduction of dose. For additional details refer to section 4.2.1.

2403 mg daily (801 mg tid) pirfenidone may be reduced to 1602 mg daily (534 mg tid) to manage adverse events (in Group 2 only). If dose reduction is required for pirfenidone then the patient must have 7 stable days at the reduced dose along with the nintedanib for the second PK day. Further dose reductions for pirfenidone are not permitted within the trial. If the patient has tolerability issues they should contact the Investigator immediately.

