	possibility to reduce to two capsules tid (534 mg tid / 1602 mg daily) Day 16 three capsules in the morning only (801 mg, this is the last dose		

Boehringer Ingelheim BI Trial No.: 1199.229 c03463451-08

Trial Protocol Version 4.0

Page 5 of 118 Proprietary confidential information © 2016 Boehringer Ingelheim International GmbH or one or more of its affiliated companies

h			
Name of company:			
Boehringer Ingelheim	1		
Name of finished product:	:		
Ofev®			
Name of active ingredient	:		
Nintedanib			
Protocol date:	Trial number:		Revision date:
17 July 2015	1199.229		29 July 2016
	in the PK period)		
Mode of administration:	Ande of administration: Oral administration with food		
Duration of treatment:	16 days		
Endpoints	Pharmacokinetic Parameters:		
	Group 1:		
	Primary endpoints: AUC _{0-tz} and C _{max} of nintedanib		
	Secondary endpoin	ts: $AUC_{0-\infty}$ of nintedanib	
	Group 2:		
	Primary endpoints.	AUC and Cmar as of nirfenid	one
	1 mary enupoints. $100_{\tau,ss}$ and $C_{max,ss}$ of phreindone		
Safety criteria:	Incidence and intensity of adverse events, physical examination, vital		
	signs, ECG, change from baseline in laboratory parameters		
Statistical methods:	Descriptive statistics and analysis of variance (ANOVA) for AUC _{0-tz} ,		
	C_{max} and AUC _{0-∞} of nintedanib with and without the association with		
	pirfenidone (group	1) and for AUC _{τ,ss} and C _{max,ss} if	for pirfenidone with
	and without the ass	ociation with nintedanib (grou	p 2).

Page 6 of 118

63451-08Trial Protocol Version 4.0Page 6 ofProprietary confidential information © 2016 Boehringer Ingelheim International GmbH or one or more of its affiliated companies

FLOW CHART - GROUP 1

Trial Periods	Screening Period ¹	PK e	valuation	n Period ¹⁰	PK Follow-up Period ¹⁸
Visit	1	2	Phone call ⁶	3 ¹³	4
Weeks		0	2	311	7
Days	-28 to -1	1-2	15	23-24	52
Time window for visits			+	6 days	+3 days
Informed consent ²	Х				
Demographics	Х				
Medical history	Х				
Review of in-/exclusion criteria	Х	Х			
Drug and alcohol testing at site	Х	Х			
Physical examination	Х	Х		Х	Х
Vital signs ³	Х	Х		Х	Х
Laboratory tests	X			Х	Х
Pregnancy test (urine) ⁹	Х	Х		Х	Х
PK sample ⁷		X^{17}		X^{17}	
		Х			
		X ¹⁴		X^{14}	Х
		X^{14}		X^{14}	
12 lead-Electrocardiogram (ECG)	X				Х
Spirometry ¹²	X	Х		Х	Х
DLCO ¹⁹	X	$(X)^{19}$			
Register screening / start of treatment	X	Х			
Dispense trial drugs ⁴		X ¹⁷		Х	
Collect trial drug & compliance check				Х	
Dispense and/or collect & review diary ⁵		X^{17}		Х	

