4.2.1.2 Recommendations for managing diarrhoea

Symptomatic treatment should be initiated at first signs or symptoms of diarrhoea (hydration, antidiarrhoeal treatment e.g. loperamide).

- Interruption of nintedanib should be considered (at the discretion of the investigator; for • patients in Group 2) to allow for resolution of symptoms.¹
- If diarrhoea persists: dose reduction or interruption of pirfenidone should be considered • (at the discretion of the physician) to allow for resolution of symptoms.¹
- 4.2.1.3 Recommendations for managing phototoxicity and/or rash (PK evaluation period only)
 - Symptomatic treatment should be considered at first signs or symptoms of • phototoxicity/rash
 - Dose reduction or interruption of pirfenidone should be considered (at the discretion of the investigator) to allow for resolution of symptoms.¹
 - After resolution of phototoxicity/rash, re-introduction and re-escalation of pirfenidone should be considered on a stepwise approach.¹

• If phototoxicity/rash persists despite dose adjustment, permanent discontinuation of pirfenidone should be considered.

Footnote:

¹ If dose reduction, interruption or re-escalation does not allow for 7 consecutive stable days prior to Visit 3 for Group 1 patients or Visit 3a or Visit 3b for Group 2 patients then the patient should stop all trial medication during the PK evaluation period and return to clinic for Visit 3 (Group 1) or visit 3b (Group 2) as per Figure 4.1.4:1.

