The PK evaluation period for this group is for a minimum of 16 days plus 28 days follow-up and begins at Visit 2.

Visit 2 Day 1

- Review concomitant therapy and any adverse events since screening.
- A drug and alcohol test will be done at the clinic.
- Physical examination and vital signs.
- Urine pregnancy test for women of childbearing potential.
- Spirometry
- Reassessment of inclusion/exclusion criteria.
- •
- Registration of treatment start by emailing the form provided in the ISF to the sponsor.
- No PK samples are taken on this day.
- Dispense two wallets of pirfenidone and instruct the patient to take 801mg tid, the first dose should be given at the clinic with food and a glass of water.
- Provide patient with dosing instructions.
- Dispense diary.
- Remind patient of Visit 3a scheduled for Day 8.

Visit 3a Day 8

Once the patient has been on stable, full dose pirfenidone for 7 days (a 3 day window is allowed to ensure 7 consecutive days) they will return to clinic for the first PK day.

The patient should attend the clinic at approximately 07:00 so that the following assessments can be started before breakfast is given:

- Physical examination and vital signs.
- Urine pregnancy test for women of childbearing potential.
- Blood sample for laboratory tests (Section 5.3.3)

- Pre-dose PK samples should be taken according to PK Flowchart (Group 2, this should be taken prior to the other blood samples).

•

- Spirometry.
- Review concomitant therapy and any adverse events since previous visit and throughout the day at regular intervals.
- Patients will return all unused medication. Medication compliance will be assessed by counting returned (unused) capsules.
- The patient will return the diary card and this will be reviewed to check that the patient has received seven consecutive, stable days of treatment.
- Three 267 mg pirfenidone capsules should be given to the patient at 08:00 during breakfast (See PK Flowchart Group 2).
- PK samples should be taken according to PK Flowchart (Group 2).
- The patient should be given lunch at 12:00.
- Three 267 mg pirfenidone capsules will be given to the patient at 14:00 with a snack.
- After the PK time point at 14:00, the patient can leave the clinic.
- The patient should be given the remaining pirfenidone from the previous visit and also one new wallet of pirfenidone and one bottle of nintedanib to take home.

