- The patient should take the final dose of three 267 mg pirfenidone capsules at home at approximately 20:00 with food and a glass of water.
- The patient should be reminded to take pirfenidone and nintedanib from Day 9 at home for seven consecutive days.
- Remind patient of Visit 3b scheduled for Day 16.

Once the patient has received nintedanib and pirfenidone for 7 consecutive days, they will return to clinic for Visit 3b for the next PK day. If the patient needs to dose reduce the pirfenidone then this is allowed see Section 4.1.4.

Visit 3b Day 16

Once the patient has been on stable, pirfenidone and nintedanib for 7 days (a 3 day window is allowed to ensure 7 consecutive days) they will return to clinic for the next PK day.

The patient should attend the clinic at approximately 07:00 so that the following assessments can be started before breakfast is given:

- Physical examination and vital signs.
- Urine pregnancy test for women of childbearing potential.
- Blood sample for laboratory tests (Section 5.3.3)
- Predose PK samples should be taken according to PK Flowchart (Group 2, this should be taken prior to the other blood samples).
- •
- Spirometry.
- Review concomitant therapy and any adverse events since previous visit and throughout the day at regular intervals.

63451-08Trial Protocol Version 4.0Page 61 of 118Proprietary confidential information © 2016 Boehringer Ingelheim International GmbH or one or more of its affiliated companies

- Patients will return all unused medication. Medication compliance will be assessed by counting returned (unused) capsules.
- The patient will return the diary card and this will be reviewed to check that the patient has received seven consecutive, stable days of treatment.
- One 150mg nintedanib capsule and three 267 mg pirfenidone capsules should be given to the patient at 08:00 during breakfast (See section 10.2; this will be the last study medication that the patient will receive in the PK evaluation period of the trial).
- PK samples should be taken according to PK Flowchart (Group 2).
- The patient should be given lunch at 12:00.
- After the PK time point at 14:00, the patient can leave the clinic.
- No study drugs are given.
- Remind patient of PK FU visit scheduled for 28 days after this visit.

PK Follow-up/ End of Trial

The patient should return to the clinic 28 days or more after Visit 3b Day 16 for their PK Follow-up/ End of Trial Visit as detailed in section 6.2.3.

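### Group 2 lets the pirfenidone dose fall between its two PK days, and no visible rule says how such an unequal-dose pair enters the un-normalised primary ratio

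*Protocol*

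**What the plan says.** **Reduction is allowed.** Protocol 4.1.4.1 permits Group 2 patients to go from 801 to 534 mg tid for adverse events and requires that "the patient must have 7 stable days at the reduced dose along with the nintedanib for the second PK day". The synopsis gives a "possibility to reduce to two capsules tid (534 mg tid / 1602 mg daily" for Days 1–15. Group 2 flow-chart footnotes 4 and 12 and Protocol 4.1.4 allow 534 mg tid in the combination week, and 6.2.2 repeats the permission after Visit 3a. The footnote to 4.2.1 stops a patient only "If dose reduction, interruption or re-escalation does not allow for 7 consecutive stable days" before the visit. No visible text requires the same dose on both PK days or a repeat of Visit 3a.

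**The PK-day dose is not stated consistently.**
- Visit 3a: 4.1.4 gives "801mg pirfenidone (or 534mg if they have dose reduced", but 6.2.2 gives "Three 267 mg pirfenidone capsules should be given to the patient at 08:00 during breakfast".
- Visit 3b: 4.1.4 gives "801mg pirfenidone and they will also receive one 150 mg capsule of nintedanib at the clinic with" food, and 6.2.2 gives "One 150mg nintedanib capsule and three 267 mg pirfenidone capsules should be given to the patient at 08:00 during breakfast". Neither has a 534 mg option.
- Table 4.1.1:2: "Group 2 Days 1-15: three capsules three times a day Day 16: three capsules in the morning only". The synopsis also gives 801 mg for Day 16.

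**The analysis.** Protocol 7.1 defines R2 and T2 at 801 mg tid only. Protocol 7.3.1 models log AUC and log Cmax,ss on subject and treatment, and SAP 7.4 and 9.1 adopt this unchanged. The SAP mentions pirfenidone dose reduction for exposure (5.4.2) and in the adverse-event tables (7.8.1), not for the PK ratio.

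**The concern.** The within-patient ratio isolates the effect of nintedanib only if the pirfenidone dose is the same on both days. The plan permits it to differ and then analyses the raw parameters.

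The likely direction is one-sided. Reductions follow adverse events, Protocol 2.1 says the two drugs' side effects overlap, and nintedanib is added only from Day 9. A reduction after Visit 3a lowers pirfenidone exposure on the test day. In the result this would look like nintedanib lowering pirfenidone, which is the question Group 2 is there to answer.

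**Working it through.** **1. The plan's own precision figure.** Table 7.7:2, total gCV 30%, correlation 0.5, N = 12:
- Within-subject variance = ln(1 + 0.30²) × (1 − 0.5) = 0.0431, which is a gCV of 21%.
- Half-width with 95% assurance = t(0.95; 11) × √(2 × 0.0431) × √(χ²(0.95; 11)/11) / √12 = 1.796 × 0.2936 × √(19.675/11) / 3.464 = 0.2035.
- exp(0.2035) = 1.226, interval 82–123. The plan states 1.23 and 82–123, so the variance inputs are understood correctly.

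**2. One unequal pair.** Assume proportional exposure and no interaction. 801 mg at Visit 3a and 534 mg at Visit 3b give 534/801 = 0.667, or −0.405 on the log scale.

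**3. Group ratio.** With k such pairs among N, the geometric mean ratio is (2/3)^(k/N).
- N = 12: 0.967 (k = 1), 0.935 (k = 2).
- N = 18 (all planned patients evaluable): 0.978 (k = 1), 0.956 (k = 2).

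**4. Interval.** At gCV 21% and N = 12 (no assurance factor), 90% CI = ratio × exp(± 1.796 × √(v/12)), where v = 2 ln(1 + 0.21²) + p(1 − p) × 0.405² × 12/11 and p = k/12.

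| Handling | v | Ratio | 90% CI |
|---|---|---|---|
| k = 0 | 0.0863 | 1.00 | 0.859–1.165 |
| k = 1, included raw | 0.1000 | 0.967 | 0.821–1.139 |
| k = 2, included raw | 0.1112 | 0.935 | 0.786–1.111 |
| one pair left out (11 pairs) | 0.0863 | 1.00 | 0.852–1.174 |
| two pairs left out (10 pairs) | 0.0863 | 1.00 | 0.843–1.186 |
| normalised, 12 pairs | 0.0863 | 1.00 | 0.859–1.165 |

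In simulation (200,000 trials per setting), the 90% CI excludes 1 in about 10% of trials at k = 0 and k = 1, and in 12.5–15.7% at k = 2.

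**5. If 801 mg is given literally at Visit 3b after a 534 mg run-in.** One-compartment model: half-life 3 h (Protocol 1.2.2), doses at 08:00, 14:00 and 20:00, absorption rate 0.4–2.0 per hour (assumed).
- Compared with 801 mg throughout, AUC over 6 h is 0.933–0.970 and Cmax at the planned times is 0.946–0.970.
- At k = 1 and N = 12 the group ratio is 0.933^(1/12) = 0.994 to 0.970^(1/12) = 0.997, a shift of under 1%. The profile is then not at steady state for the dose given.

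**6. How many patients could qualify.** Visit 3b can be at Day 16 + 3 = Day 19 at the latest, which needs stable Days 12–18. Nintedanib starts on Day 9, so a reduction must begin by Day 12. Otherwise Protocol 4.1.4 says no PK samples are taken.

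**The case against.** The main counter-arguments are these.

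- **The 801 mg entries may be nominal.** Group 2 flow-chart footnote 4 speaks of the morning dose of each drug after a run-in at either dose. Protocol 4.1.4 refers to the patient's own morning dose, and 4.1.3 allows dose adjustments under 4.2. This stands: a literal 801 mg for a patient just reduced for an adverse event is a strained reading, so the wording conflict is secondary.
- **Later exclusion is possible.** SAP Table 6.2:1 may be supplemented, and SAP 7.4 provides parameter-level exclusion flags. This stands as a mechanism, but it is not a rule for this case. A permitted 534 mg dose is hardly non-compliant under Protocol 7.3, so the visible rules point towards including it.
- **Part of the plan cannot be seen.** Figure 4.1.4:1, the further endpoints and the internal PK standard to which SAP 7.4 defers are not available. One of them might hold a rule, so the claim is limited to the visible text.
- **The effect is small.** Patients enter on full dose, the timing window is short, k may be zero, and at k = 1 the ratio of 0.967 lies well within its own interval. This stands and sets the severity.

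A reader might infer that the same reduced patient could enter at 0.67, at 0.93–0.97 or not at all, depending on how the site reads the dose text. The first two arguments show why the documents do not support giving these outcomes equal weight: inclusion at about 0.67 is the main case. A reader might also expect an upward bias from 534 mg at Visit 3a and 801 mg at Visit 3b. That is possible but unlikely, because the reduction would have to start by Day 4 in patients who enter on full dose.

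**Conclusion.** The point holds on the visible text. A pair that follows the protocol, with 801 mg on the reference day and 534 mg on the test day, enters the primary analysis un-normalised and lowers the Group 2 ratio by about 3.3% per patient with 12 pairs. The estimate is then no longer the 801 mg comparison that Protocol 7.1 defines.

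The size rests on dose proportionality between 534 and 801 mg, which the documents do not state for pirfenidone, and on an unknown k. The documents do not support a claim that the trial's conclusion is wrong or that a false interaction is likely. Protocol 7.2 has no confirmatory hypothesis, 7.7 calls the trial exploratory, and one such patient leaves the chance of a CI excluding 1 at about 10%. Severity is minor to moderate, and confidence is medium because of the text that cannot be seen.

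**What to change.** 1. In the synopsis, Table 4.1.1:2, and Protocol 4.1.4 and 6.2.2, state that the pirfenidone dose at Visits 3a and 3b is the patient's current stable dose, 801 or 534 mg.
2. In the SAP, pre-specify that Group 2 AUCτ,ss and Cmax,ss are normalised to the pirfenidone dose taken that PK morning, before the log transform. Put an analysis restricted to same-dose pairs beside it. The order may be reversed, with same-dose pairs as primary.
3. Report the number of unequal-dose pairs.

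**Cost.** A clarification in four places, a few lines in the SAP and one derived variable. The amount taken on each PK morning must be recorded: Protocol 5.4.1 names only date and time, although SAP 5.4.2 already needs time on each actual dose. Equal-dose pairs keep their ratio, so nothing changes if k = 0.

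**Downside.** Normalisation assumes proportionality, and restricting to same-dose pairs loses a few pairs. If exposure varies as dose^b with b from 0.8 to 1.2 (an assumed range), the normalised ratio is (2/3)^((b − 1)k/12) and the raw ratio is (2/3)^(bk/12).
- k = 1: 1.007 to 0.993 normalised, against 0.973 to 0.960 raw.
- k = 2: 1.014 to 0.987 normalised, against 0.947 to 0.922 raw.

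The same-dose analysis checks the assumption.
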